### 9.3 Monitoring and Auditing

#### 9.3.1 Audit

At a ratio of 20%, we randomly select research centers to conduct audits to check problems encountered by researchers in data collection and by CRAs in the monitoring process. All centers are required to conduct self-inspections and make corrective actions based on the content and focus of the problems to ensure the quality of project research.

#### 9.3.2 Monitoring

Formulate a strict monitoring plan, and CRA will regularly conduct routine monitoring of the research center to check the project progress and the implementation of the researcher's plan; the authenticity of the data and the traceability of the original data, etc. And promptly require the researcher to track and correct the problems in the monitoring report.

### 9.4 Project implementation SOP and training

- (1) Formulate the SOP for this study and require that the project be implemented strictly in accordance with the corresponding SOP.
- (2) Establish a strict training system and provide project training to all project participants (project managers, CRAs, researchers, and researcher assistants, etc.).

## 10 Statistical analysis

SAS version 9.4 or above was used for data statistical analysis.

All statistical tests were two-sided, and  $P < 0.05$  was considered to be statistically significant.

The description of quantitative indicators will calculate the number of cases (N), mean (Mean), standard deviation (SD), median (Median), minimum (Min) and maximum (Max). When comparing between groups, t-test or analysis of variance was used. The description of categorical indicators uses the number of cases (N) and percentage (%) of each category. When comparing between groups, chi-square test or Fisher's exact probability method was used. The Kaplan-Meier (KM) test was used to estimate the survival function and calculate the median time for time-to-event variables. The survival curves between different groups were compared based on the Log-Rank test, and the corresponding P value was calculated.

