#### 3.1 Sample size

Routine observation: all patients that can be collected during the observation period.

Maximum observation period: 28 days.

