#### 4.4 Source of Cases

At each research center, all eligible patients will serve as observation subjects for this cohort study. Patients will be assigned to respective observation cohorts based on their actual prescription status, with enrollment for each group continuing until the target number is reached.

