### 6.2 Effectiveness Observation Items

**(1) Joint swelling and pain relief rate: After the first dose, DAS 44 score was < 1.6, and decreased by more than 0.6 before and after treatment.**

Disease Activity Score of 44 Joints Based on CRP (DAS 44 -CRP): It assesses the degree of joint swelling and pain. The calculation formula is as follows:

$$\text{DAS44 - CRP} = 0.54 \times \sqrt{RAI} + 0.065 \times \sqrt{SJC44} + 0.17 \times \ln(CRP + 1) + 0.072 \times GH + 0.45$$

**44 assessed joints:** including both hand metacarpophalangeal joints (MCP1-5), proximal interphalangeal joints (PIP2-5), thumb interphalangeal joints, both wrists, both elbows, both shoulders and both knees, as shown in the figure below:

**Swollen joint count (SJC):** The number of swollen joints among 44 joints was recorded .

**CRP level:** Record laboratory test results in mg/dL (CRP).

**VAS score:** Patients mark the disease activity on a 0-100 mm visual analog scale based on their own feelings, with 0 representing no activity and 100 representing extreme activity.

2) Disease activity grading of joint swelling and pain (based on DAS 44 score):

Low activity ( DAS 44 < 1.6 )

Moderate activity ( 1.6≤DAS44 < 2.4 )

High activity ( 2.4≤DAS 44 ≤ 3.7 )

Severe activity (DAS 44 > 3.7 )

3) Evaluation of treatment response at the time of disease remission (based on reduction in DAS 4 score):

Good response (DAS 44 >1.2)

General response (0.6<DAS 44 ≤1.2)

No response (DAS 44 ≤ 0.6)

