### 9.1.4 Control of confounding bias

The final data were controlled using statistical methods such as stratified analysis, standardization, multivariate analysis, and propensity score.

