## **11 Ethical requirements**

Since this study is an observational study, it does not interfere with normal clinical medical services, nor does it interfere with patients' medical treatment and medication behavior. Therefore, in addition to passing the ethics review at the clinical lead unit, other research centers can conduct ethics filing as needed, or conduct ethics review of this project, but the focus of the review should be the feasibility of this project in the center. After the review and approval, if major modifications to the trial protocol are required, it should be submitted to the ethics committee of the clinical lead unit for review and approval again.

Only researchers and monitors involved in clinical research may have access to the personal medical records of the research subjects, and they will include confidentiality in the signed researcher statement or confidentiality commitment. The ethics committee and the drug supervision and administration department have the right to review the clinical research records. When processing data, the data will be anonymous, omitting information that can identify the individual identity of the research subjects. The medical records of the research subjects are kept in the data archives of the drug clinical research institution with strict security and confidentiality measures.

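### Protocol section 10 names only unadjusted tests for cohorts formed by prescription, is not linked to the confounding control in 9.1.4, and leaves open which result answers objective 2

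*Protocol*

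**What the plan says.** Objective 2 (Protocol section 2) is to evaluate the effectiveness and safety of Chinese medicine. Section 4.4 forms the cohorts by treatment received: "Patients will be assigned to respective observation cohorts based on their actual prescription status". Section 11 says of the study that "it does not interfere with normal clinical medical services".

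Section 10 sets a two-sided 0.05 threshold and names the between-group methods. For quantitative outcomes, "When comparing between groups, t-test or analysis of variance was used". For categorical outcomes it names chi-square or Fisher's exact test. For times to event, "The survival curves between different groups were compared based on the Log-Rank test". It names no covariate, stratum, regression model, weighting or matching.

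Section 9.1.4, under quality control, says: "The final data were controlled using statistical methods such as stratified analysis, standardization, multivariate analysis, and propensity score". It names no outcome and no covariate, and does not mention the section 10 tests.

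**The concern.** Treatment chosen in routine care can follow the features that predict recovery. Section 5.1 lists antipyretics and NSAIDs for pain under Western care and ties Chinese treatment to syndrome differentiation, while fever and joint pain are also effectiveness outcomes in section 6.2. Imbalance is therefore plausible, though the protocol does not show it.

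If the cohorts differ prognostically, an unadjusted P value mixes that difference with any treatment effect, and for a fixed imbalance the error grows with enrolment. Adjustment is promised in one place and crude tests with a significance threshold are fixed in another. With no order between them, either result could be presented as the answer to objective 2 after both have been seen.

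**Working it through.** The protocol states no power, effect size or cohort size, so it has no figure of its own to reproduce. Section 3.1 takes "all patients that can be collected during the observation period", while section 4.4 recruits "with enrollment for each group continuing until the target number is reached" and gives no target. That mismatch is a separate matter; here it means only that cohort sizes must be assumed.

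**1. Joint relief depends on baseline by definition.** Section 6.2 requires DAS44 < 1.6 after treatment "and decreased by more than 0.6 before and after treatment". The fall must therefore exceed max(0.6, baseline − 1.6).

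- The formula's minimum, with all inputs zero, is 0.45. A patient at or below 0.45 + 0.6 = 1.05 cannot fall by more than 0.6, and so cannot meet the endpoint.
- Up to a baseline of 1.6 + 0.6 = 2.2, the required fall is 0.6.
- Above 2.2 it rises: 0.8 at 2.4, 1.4 at 3.0 and 2.1 at 3.7.

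**2. Relief by activity band with the same treatment effect for everyone.** Assumptions: baseline uniform within each band, a floor of 0.45, and a normally distributed fall. The fall is either additive (mean 1.2, SD 0.6 to 1.0) or proportional (mean 50%, SD 20 to 30%). Relief is the average over the band of P(fall > required fall).

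| Band | Additive | Proportional |
|---|---|---|
| Low (0.45–1.6) | 35–40% | 26–28% |
| Moderate (1.6–2.4) | 72–83% | 73–82% |
| High (2.4–3.7) | 36–41% | 54–56% |

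Relief is strongly tied to baseline but does not move in one direction. The moderate-to-high gap is 31 to 47 points (additive) or 19 to 26 points (proportional). The severe band (above 3.7) is not modelled.

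**3. Rash change depends on illness day at entry.** Section 4.1.1 places rash 2 to 5 days into the illness, section 4.2 admits patients up to 3 days after onset, and section 6.2 scores change from baseline on days 3 and 5. A patient entering at onset is scored on illness days 3 and 5, against a baseline that precedes the expected rash. A patient entering 3 days after onset is scored on illness days 6 and 8, against a baseline that may already include rash. No figure can be put on this from the protocol.

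**4. What this can do to the crude test (illustration only).** Assumptions: no treatment effect, three equal cohorts, moderate and high bands only, and adjustment under 9.1.4 not applied. With high-band share s_k in cohort k and relief r0 (moderate) and r1 (high):

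- p_k = (1 − s_k)·r0 + s_k·r1
- noncentrality = Σ n(p_k − p̄)² / [p̄(1 − p̄)], referred to a noncentral chi-square with 2 df and critical value 5.991.

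Example: r0 = 0.70, r1 = 0.40, s = 0.20, 0.35, 0.50, n = 200 per cohort. Then p = 0.64, 0.595, 0.55 and p̄ = 0.595. Noncentrality = 200 × (2 × 0.045²) / (0.595 × 0.405) = 0.81 / 0.241 = 3.36, and the rejection probability is 35.6%.

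Rejection at 100 / 200 / 400 per cohort:

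| High-band shares | Extreme imbalance | Relief 65% vs 45% | Relief 70% vs 40% |
|---|---|---|---|
| .30, .35, .40 | 10 points | 5.6 / 6.3 / 7.6% | 6.4 / 7.9 / 11.1% |
| .25, .35, .45 | 20 points | 7.6 / 10.3 / 16.1% | 11.1 / 17.8 / 32.0% |
| .20, .35, .50 | 30 points | 11.0 / 17.6 / 31.7% | 19.5 / 35.6 / 63.7% |

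The spurious difference between the extreme cohorts is imbalance × gap. At 30 points it is 0.30 × 20 = 6 points or 0.30 × 30 = 9 points.

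**The case against.** The strongest reply is that section 9.1.4 already commits, without condition, to confounding control. Section 10 does not say its tests are the only analysis, and choosing a lead method and its covariates is ordinary SAP work. Much of this stands. The protocol is not silent on confounding, the two sections do not contradict each other, and covariate lists and model details are not missing from it.

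It does not dispose of the point. Section 10 does not defer the choice: it fixes crude tests and a significance threshold for cohorts that nothing balances. An open list under quality control, tied to no outcome, does not say which kind of result answers the protocol's own objective.

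A reader might also infer three stronger things that the documents do not support:

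- **That the study will rely on crude tests alone, with false-positive rates of up to 64%.** That figure ignores 9.1.4, models two of four bands and takes the largest assumed imbalance, gap and cohort size.
- **That a cohort with lower baseline joint activity would show more relief.** With the 0.45 floor this fails in general. Low-band relief is below moderate-band relief under both models, and below high-band relief under the proportional one.
- **That the cohorts will differ.** The protocol gives no information on baseline DAS44 or illness day by cohort.

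**Conclusion.** The point holds as a badly fixed statement in the protocol and is worth correcting. Section 10 attaches P < 0.05 only to unadjusted comparisons of prescription-formed cohorts, 9.1.4 is not linked to it, and nothing ranks the two for objective 2. At least two effectiveness endpoints depend on status at entry through the protocol's own definitions.

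The size of any bias is unknown. Under the assumptions of step 4, the crude test alone rejects about 6 to 11% of the time at a 10-point imbalance and 11 to 64% at a 30-point imbalance, with 100 to 400 per cohort. These figures show sensitivity to imbalance and do not forecast this study's error rate. An SAP, if one exists, may already settle the ranking.

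**What to change.** State in section 10 that the main effectiveness comparison for objective 2 is confounder-adjusted, using one method from 9.1.4, for example regression or three-group propensity-score weighting. Base it on baseline covariates the protocol already collects, including time since onset and the baseline value of the score being analysed, and fix them before outcome data are seen. Label the t-test/ANOVA, chi-square/Fisher and log-rank results descriptive, and cross-refer sections 10 and 9.1.4. Model details can go in the SAP.

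The cost is two or three sentences, a cross-reference and some programming. Precision may suffer if the cohorts overlap poorly on the covariates. Adjustment deals only with measured confounders, so conclusions on effectiveness would still need that caveat.

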## 9.2 Program design and sample representativeness assurance

To ensure that the cases can represent the patients using Jingfang Heji, a multi-stage sampling method was used to select an estimated 10 hospitals from different regions and levels as case collection hospitals according to the regional distribution of clinical sales of Jingfang Heji and the hospital grade

distribution, as well as the sales share of hospitals of different grades. Based on the previous cases of using Jingfang Heji, a quota was used to allocate the sample size.

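### Section 10 fixes group tests without hospital in a multi-centre cohort; if treatment mix differs by hospital and outcomes correlate within hospital, P values are too small

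*Protocol*

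**What the plan says.** Protocol Section 10 names the between-group tests by type of outcome:

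- Quantitative: "When comparing between groups, t-test or analysis of variance was used".
- Categorical: "When comparing between groups, chi-square test or Fisher's exact probability method was used".
- Time to event: "The survival curves between different groups were compared based on the Log-Rank test".

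The threshold is P < 0.05, two-sided. No hospital term, stratum, random effect or cluster-robust variance appears.

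The study has more than one centre. Section 4.4 states "At each research center, all eligible patients will serve as observation subjects for this cohort study" and places patients in cohorts by what they were actually prescribed. Section 9.3.1 audits a random 20% of centres, and Section 11 sets ethics arrangements for centres other than the lead unit.

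Section 9.2 adds that "a multi-stage sampling method was used to select an estimated 10 hospitals from different regions and levels as case collection hospitals". That paragraph opens with a different aim, "To ensure that the cases can represent the patients using Jingfang Heji", and the product is named nowhere else in the protocol.

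Section 9.1.4 says confounding is controlled by methods such as stratification, standardization, multivariate analysis and propensity scores. It mentions neither hospital nor clustering.

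**The concern.** Every test listed in Section 10 assumes independent patients. Two features of the study can break that assumption in a way that matters.

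First, outcomes may correlate within hospital. Swollen-joint counts and rash severity are rated by assessors (Section 6.2). The closing laboratory and RNA tests fall on D5 or before discharge (Section 5.2), so local discharge habit can affect the recorded times to negative conversion and to white-cell and platelet recovery.

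Second, treatment follows prescription, and nothing in the design balances the three cohorts within a hospital.

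If both hold, two harms follow. The unadjusted standard error is too small, so the nominal 5% test rejects too often. And a difference between hospitals in case mix, assessment or discharge practice can be reported as a difference between treatments.

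**Working it through.** The protocol gives no sample size, ICC, number of patients per hospital or treatment mix by hospital, so it has no figure to reproduce. What can be checked is how far the stated 5% level may move under assumed values.

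**Inputs from the protocol:** two-sided alpha 0.05; unadjusted tests (Section 10); several centres (Sections 4.4, 9.3.1, 11).

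**Assumed:** ICC 0.01 to 0.10; m = 20, 50 or 100 patients per hospital; 10 hospitals in the simulation (the Section 9.2 estimate); two groups and a normal outcome for simplicity.

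**Step 1, the extreme case: hospital alone decides treatment.**

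Design effect DE = 1 + (m − 1) × ICC. Real error rate = 2 × [1 − Φ(1.96/√DE)].

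For example, with m = 50 and ICC 0.05, DE = 1 + 49 × 0.05 = 3.45, 1.96/√3.45 = 1.055, and the error rate is 0.291.

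| m | ICC 0.01 | ICC 0.05 | ICC 0.10 |
|---|---|---|---|
| 20 | DE 1.19, 7.2% | DE 1.95, 16.0% | DE 2.90, 25.0% |
| 50 | DE 1.49, 10.8% | DE 3.45, 29.1% | DE 5.90, 42.0% |
| 100 | DE 1.99, 16.5% | DE 5.95, 42.2% | DE 10.9, 55.3% |

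**Step 2, intermediate mixes.** Simulation under no treatment effect: 4000 runs per setting, 10 hospitals, m = 50, ICC 0.05. Half the hospitals have one treatment share and half the other. The hospital-adjusted analysis is a fixed hospital effect, or a t-test on hospital means where each hospital uses one treatment.

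| Treatment share in the two sets of hospitals | Unadjusted t-test | Hospital-adjusted |
|---|---|---|
| 50% in all | 5.3% | 5.4% |
| 30% / 70% | 9.6% | 5.1% |
| 10% / 90% | 21.5% | 5.2% |
| 0% / 100% | 29.4% | 5.3% |

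The Monte Carlo standard error at 5% is √(0.05 × 0.95/4000) = 0.3 percentage points.

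**Step 3, arithmetic cross-check.** In a partial mix, the clustering term shrinks by the share of treatment variance lying between hospitals, r = (p − 0.5)²/0.25, so DE = 1 + (m − 1) × ICC × r.

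- 30/70: r = 0.04/0.25 = 0.16; DE = 1 + 49 × 0.05 × 0.16 = 1.392; 1.96/√1.392 = 1.661; error rate 9.7%.
- 10/90: r = 0.16/0.25 = 0.64; DE = 1 + 49 × 0.05 × 0.64 = 2.568; 1.96/√2.568 = 1.223; error rate 22.1%.
- Even mix: r = 0; DE = 1; error rate 5%.

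These agree with the simulation. The inflation needs both an ICC above zero and a treatment mix that differs by hospital, and it grows with each. Over all simulated settings (m = 20 and 50, ICC 0 to 0.10), the hospital-adjusted analysis stayed at about 4% to 6%.

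**The case against.** **Centre effects belong in the SAP.** Centre terms and variance estimators are often left there, and no SAP is at hand. Silence on hospital would then be no fault. But Section 10 is not silent on the tests: it names them for each type of outcome and sets the significance level, and an SAP that followed it would inherit the problem. The point is limited to those stated tests.

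**Section 9.1.4 already covers it.** Stratified or multivariate analysis could include hospital. It is not said to, and Section 10 takes up none of these methods. Adjusting for patient covariates alone also does not correct standard errors for clustering. The objection does show that the gap is wider than hospital: the two sections need reconciling.

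**The sampling design is doubtful.** This stands. A reader might take from Section 9.2 that patients come from a multi-stage sample of about 10 hospitals. That paragraph selects hospitals by sales of a product that is in no cohort definition, and it allocates the sample by quota, whereas Section 3.1 takes all patients who can be collected. It is weak evidence of how this study obtains patients. Several centres are established without it.

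**The key condition is not in the protocol.** This also stands. A reader might infer that the P values are certainly too small, or that the error rate is 7% to 29% (the Step 1 range for 20 to 50 patients per hospital and ICC 0.01 to 0.05). Those rates apply only if hospital wholly decides treatment. The protocol assigns cohorts patient by patient and nowhere says that hospitals differ in modality.

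**Conclusion.** The point holds in conditional form. Section 10 commits to unadjusted tests in a non-randomised, multi-centre cohort and does not carry through the control promised in Section 9.1.4. If treatment mix differs by hospital and outcomes correlate within hospital, the P values are too small and hospital differences enter the treatment contrast.

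The size is illustrative. At an assumed ICC of 0.05 and 50 patients per hospital, it runs from no inflation with an even mix, through about double the nominal rate at 30/70, to nearly six times when hospital alone decides treatment (29.4/5 = 5.9). Smaller hospitals or a lower ICC give less, and larger values give more. Where any one outcome in this study falls cannot be determined from the document.

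**What to change.** Revise Section 10 so that the between-group comparisons are adjusted for hospital, in line with Section 9.1.4:

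- Quantitative outcomes: a linear model with hospital as a fixed or random effect, in place of the t-test or ANOVA.
- Categorical outcomes: a Cochran-Mantel-Haenszel test or a logistic model with hospital, in place of chi-square or Fisher.
- Time-to-event outcomes: a log-rank test stratified by hospital.

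Name hospital explicitly in Section 9.1.4, and report the treatment mix by hospital so that a reader can see how much within-hospital comparison exists. Reconcile Section 9.2 with Sections 3.1 and 4.4 on how hospitals and patients are obtained.

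State the limit as well. A hospital that uses only one modality adds no information to the stratified contrasts. Hospital-level standard errors with a small-sample correction can repair the error rate there, but cannot separate hospital from treatment. If there are 10 hospitals, three groups and one modality in each, only 10 − 3 = 7 degrees of freedom remain.

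The change needs analysis wording and the centre identifier, with no new measurements. The price is wider confidence intervals and some loss of information from one-modality hospitals.

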**(2) Rash scores compared with baseline: Changes in rash scores compared with baseline on days 3 and 5 after medication ;**

Affected area : The maximum affected area of each body part is 100% , and the affected area is locally scored according to the following table, 0-6.

Affected area	0	1-9%	10 - 29%	30 - 49%	50 - 69%	70 - 89%	90 - 100%
Local scoring	0	1	2	3	4	5	6

Clinical symptom score: The severity of each symptom is rated from 0 to 3:

Severity of illness	none	light	middle	Heavy
score	0	1	2	3
✓ The average severity of the affected area. Half-grade points can be recorded between each symptom grade, e.g. 2.5.				

Erythema: 0 = none; 1 = mild (barely visible, pink); 2 = moderate (clearly visible, dark red); 3 = severe (deep red or fiery red)

Papules: 0 = none; 1 = mild (barely noticeable raised areas); 2 = moderate (clearly visible raised areas but not prominent); 3 = severe (prominent raised areas)

Rash Scoring Scale:

Body Parts	erythema (0-3)	Edema / pimples (0-3)	Local scoring (0-6)	Body Parts Score

neck	( +	+	)	
trunk	( +	+	)	
Upper limbs	( +	+	)	
Lower limbs	( +	+	)	

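### Section 10 tests rash change and joint relief without adjusting for the D0 score in cohorts formed by prescription, so a D0 difference alone can move both results

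*Protocol*

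**What the plan says.** Protocol section 10 gives one rule per type of outcome. For quantitative indicators: "When comparing between groups, t-test or analysis of variance was used". For categorical indicators: "When comparing between groups, chi-square test or Fisher's exact probability method was used". It names no covariate and no regression model. Tests are two-sided at 0.05.

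Two of the first three effectiveness outcomes in section 6.2 are defined relative to D0. The rash outcome is "Changes in rash scores compared with baseline on days 3 and 5 after medication". Joint relief is a responder outcome: "After the first dose, DAS 44 score was < 1.6, and decreased by more than 0.6 before and after treatment".

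The cohorts are not randomised. Section 4.4 says: "Patients will be assigned to respective observation cohorts based on their actual prescription status".

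On confounding, section 9.1.4 says: "The final data were controlled using statistical methods such as stratified analysis, standardization, multivariate analysis, and propensity score". It names no covariate, outcome or model, and section 10 does not refer to it.

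**The concern.** Prescribing is likely to follow how ill the patient is at presentation, so D0 differences between the Chinese medicine, Western medicine and integrated cohorts should be expected. Subtracting D0, or requiring a fall from D0, does not remove the effect of such a difference.

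For rash, patients who start higher tend to fall further unless the follow-up score rises one for one with the D0 score. For joints, the two-part criterion makes the chance of relief depend on D0. In both cases a D0 gap can appear as a treatment difference or hide one. For rash, leaving D0 out of the model can also waste precision.

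**Working it through.** **Inputs.** From the Protocol: the tests and the two-sided 0.05 level (section 10), the two outcome definitions (section 6.2), and allocation by prescription (section 4.4). The Protocol gives no sample size, SD, correlation or D0 distribution, so there is no stated figure to reproduce. Everything numerical below is assumed, with ranges.

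**1. Rash: shift from a D0 gap.** Suppose the cohorts have the same expected follow-up score given D0, with slope b of follow-up on D0 and a D0 gap g. With no treatment effect, the difference in mean change is (b − 1) × g. With equal SDs at D0 and follow-up, b = rho, and the higher cohort shows an extra fall of (1 − rho) × g.

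Take g = 0.3 SD and n = 100 per cohort. The standard error of the difference in change is √(2 × 2(1 − rho)/n), in SD units.

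| rho | shift (SD) | standard error | ratio | chance of P < 0.05 |
|---|---|---|---|---|
| 0.3 | 0.21 | 0.167 | 1.25 | 24% |
| 0.5 | 0.15 | 0.141 | 1.06 | 19% |
| 0.7 | 0.09 | 0.110 | 0.82 | 13% |

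The last column is Φ(ratio − 1.96) + Φ(−ratio − 1.96); it should be 5%. At a gap of 0.5 SD it becomes 55%, 42% and 28%.

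**2. Rash: precision.** With equal SDs, the change score has variance 2(1 − rho)s² and the covariate-adjusted score (1 − rho²)s². The ratio is (1 + rho)/2 = 0.65, 0.75 and 0.85 at rho 0.3, 0.5 and 0.7. A comparison with 80% power on the change score would then have Φ(2.80 × √(2/(1 + rho)) − 1.96), about 93%, 90% and 86%, if D0 is nearly balanced.

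Two limits apply.
- The gain vanishes as the slope nears 1. With follow-up SD twice the D0 SD and rho = 0.5, the slope is 0.5 × 2 = 1. The change variance is 1 + 4 − 2 = 3 and the adjusted variance 4 × (1 − 0.25) = 3, so nothing is gained. The shift in step 1 is then also zero.
- A D0 gap costs the adjusted analysis a factor 1 + g²/4 with equal cohorts. At g = 0.5 SD this is 1.06, and at rho = 0.9 it cancels the gain (change-to-adjusted variance ratio 0.99).

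**3. Joint relief: where D0 acts.** A patient responds if follow-up DAS44 is below both 1.6 and D0 − 0.6. The two limits meet at D0 = 1.6 + 0.6 = 2.2. Below 2.2 the required fall is the harder condition and eases as D0 rises; above 2.2 the 1.6 limit is the harder one and bites more as D0 rises.

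For illustration, let follow-up be 0.5 × D0 plus a normal error of SD 0.4 (floor 0.45), with D0 SD 0.7 and the same treatment effect in both cohorts. Raise one cohort's D0 mean by 0.35:

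| D0 mean, lower cohort | relief, lower cohort | relief, higher cohort |
|---|---|---|
| 1.4 | 48% | 60% |
| 1.6 | 55% | 65% |
| 2.0 | 66% | 68% |
| 2.2 | 68% | 66% |
| 2.8 | 61% | 50% |

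A second model shows the same pattern (normal scores, SD 0.8, mean fall 0.8, correlation 0.5, D0 gap 0.4): +5.8 percentage points from a D0 mean of 1.4, 0.0 from 2.0, and −4.8 from 2.8.

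**The case against.** The strongest reply is that section 9.1.4 already promises multivariate and propensity-score control, that baseline severity is an obvious term in such models, and that covariate lists usually belong in the statistical analysis plan. Part of this stands: the Protocol need not list every covariate, and section 10 does not say its tests are the only comparisons. But section 10 does fix the between-group tests for these outcomes, and they are unadjusted. A propensity model without D0 rash or D0 DAS44 would satisfy 9.1.4 and leave the problem in place.

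A second reply is that in non-randomised cohorts the change score is not biased if the cohorts would have changed in parallel; the adjusted analysis would then be the biased one. This stands as a condition on step 1. Parallel change is doubtful for a self-limiting rash scored down to a floor of 0, but the Protocol cannot settle it.

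A reader might also infer three stronger claims that the documents do not support.
- That the tests ignore D0 altogether. They do not: D0 is subtracted in the rash change and enters the required fall in DAS44. What is missing is adjustment for it as a covariate.
- That the same imbalance must push rash and joint relief in opposite directions. That needs D0 DAS44 mostly above about 2.2, and no D0 distribution is given. Section 6.2 itself defines low (below 1.6) and moderate (1.6 to below 2.4) activity bands, where the shift can be nil or in the same direction as rash.
- That the change score is less precise at any correlation below 1. That requires equal SDs and little imbalance. Rash is said to appear 2 to 5 days after onset (section 4.1.1) and enrolment is within 3 days (section 4.2), so the follow-up SD may well exceed the D0 SD.

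**Conclusion.** The point holds in a limited form. Section 10 fixes tests that do not adjust for D0, in cohorts where D0 differences are to be expected, and 9.1.4 is not carried into section 10.

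For rash, a modest D0 gap raises the false-positive rate from 5% to between 13% and 24%. This rests on equal SDs, a 0.3 SD gap, 100 per cohort, correlation 0.3 to 0.7, and cohorts sharing the same expected follow-up score given D0. For joint relief, the illustrated shift runs from 12 points up to about 11 points down, and its sign depends on where D0 DAS44 lies relative to 2.2. The precision gain on rash is real with equal SDs and little imbalance, but is not guaranteed. This is worth correcting before the analysis; it does not invalidate the study.

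**What to change.** In section 10:

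- Analyse the day-3 and day-5 rash scores by analysis of covariance with cohort and D0 rash score, reporting the adjusted mean difference with its 95% confidence interval.
- Analyse joint relief by logistic regression with cohort and D0 DAS44, reported as a standardised risk difference. Enter D0 DAS44 flexibly, for example as a spline, because a single linear term cannot follow a response that rises and then falls around 2.2.
- Keep the t-test/ANOVA and chi-square/Fisher results as descriptive.

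In section 9.1.4, name the D0 rash score and D0 DAS44 among the terms of the multivariate or propensity models, and refer to that section from section 10.

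The cost is wording only, since both outcomes already require the D0 values. The downside is that adjusted and change-score results can differ in non-randomised cohorts, so both should be shown with the assumption behind each. Measurement error in the D0 scores will leave some residual bias.
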